1.0 Background

Inability of the surgeon to identify or localize the diseased PG can occur in 5 – 10% of cases resulting in failed parathyroidectomies (1, 2). As a result, persistent hyperparathyroidism can occur in these patients resulting in unnecessary repeat surgeries that may be associated with increased morbidity and costs (3, 4). Ultrasound imaging, ^{99m}Technetium-sestamibi scintigraphy, and computed tomography (CT) have so far demonstrated variable efficacy in preoperative localization of diseased PGs (5, 6) and may not always correlate well with the surgical field of view as observed intraoperatively. Consequently, most surgeons rely on visual identification of PGs during surgery, whereby the accuracy of PG identification is eventually determined by her/his surgical skill and experience (7, 8). When in doubt, a surgeon routinely confirms the identity of PG tissue intraoperatively by sending the specimen for frozen section analysis (or PTH aspirate) that typically requires a wait time of 20–30 minutes per sample (9) and has additional costs.

By easily being able to distinguish parathyroid from other tissues intraoperatively, postsurgical complications and associated costs may be reduced. The unique discovery of near infrared autofluorescence (NIRAF) in parathyroid tissues demonstrated that optical modalities that detect NIRAF can be utilized for non-invasive and label-free identification of parathyroid tissues with an accuracy as high as 97%.(10, 11, 12, 13) Since then, several research groups have explored the feasibility of localizing parathyroid glands using NIRAF detection with reasonable success, resulting in FDA clearance for this optical technique (14). In this study, we plan to evaluate whether an FDA-cleared device called 'PTeye' (███████████) is beneficial or not, for the surgeon and patient during parathyroid operations. The results of such a study will help us to understand and assess the true impact of optical modalities such as PTeye on (i) improving the quality and efficiency of parathyroid surgeries and (ii) minimizing risk of postsurgical complications and related expenses.

2.0 Rationale and Specific Aims

The goal of this study is to assess whether using PTeye – a NIRAF detection modality – can reduce healthcare associated costs after parathyroid surgeries and improve patient outcomes. The specific aims of this study is to determine if PTeye is beneficial or not for (i) intraoperative identification of parathyroid tissues, (ii) improving efficiency of parathyroid surgeries, and (iii) minimizing risk of postsurgical complications.

By being able to quickly and definitively locate parathyroid glands while in the operating room, the duration of surgical procedure could be further reduced. In addition, the number of frozen section biopsy (or PTH aspirate) and associated costs can be minimized. Furthermore, repeat surgeries as a result of missing a diseased parathyroid gland at the time of the initial parathyroidectomy for hyperparathyroidism could potentially be avoided.

Primary Outcome Measure:

1. Number of frozen sections (or PTH aspirate) sent for analysis
 - a. Number of frozen sections (or PTH aspirate) sent for analysis during the procedure to confirm potential parathyroid tissue [Time Frame: Immediate. During PTx procedure.]

Secondary Outcome Measure:

1. Persistent hyperparathyroidism (Immediate)

- a. Failure of intra-operative parathyroid hormone (PTH) to normalize (defined as failure of PTH to drop > 50% of its baseline value at final intra-operative PTH assay and/or failure of PTH to drop < 65 pg/ml or 6.9 pmol/L). [Time Frame: During parathyroidectomy (PTx) procedure]
- 2. Persistent hyperparathyroidism or hypercalcemia (transient)
 - a. Elevated blood calcium levels (total blood calcium level > 10.5 mg/dL or 2.6 mmol/L) with/without elevated parathyroid hormone (PTH) (serum intact PTH > 65 pg/ml or 6.9 pmol/L) at first postoperative visit. [Time Frame: 5-14 days after PTx procedure]
- 3. Persistent hyperparathyroidism or hypercalcemia (failed parathyroidectomy)
 - a. If blood calcium with/without parathyroid hormone (PTH) has not normalized at 1st post-operative visit, calcium and/or PTH is subsequently measured as necessary. Patient is defined to have a failed parathyroidectomy if hypercalcemia/hyperparathyroidism (defined as total blood calcium level > 10.5 mg/dL or 2.6 mmol/L, with/without elevated serum intact PTH > 65 pg/ml or 6.9 pmol/L) persists at or after the 6th postoperative month. [Time Frame: 6 months after PTx procedure]
- 4. Overall number of parathyroid glands identified
 - a. Overall number of parathyroid glands identified (Experimental Group: Glands identified with naked eye + NIRAF; Control Group: Glands identified with naked eye) [Time Frame: Immediate. During PTx procedure.]
- 5. Number of parathyroid glands identified with NIRAF
 - a. Number of parathyroid glands identified with NIRAF, which was not seen with surgeon's naked eye [Time Frame: Immediate. During PTx procedure.]
- 6. Number of diseased parathyroid glands identified versus preoperatively localized glands
 - a. Number of diseased parathyroid glands identified intra-operatively versus glands localized preoperatively using sestamibi, CT or ultrasound [Time Frame: Preoperative to immediate during PTx procedure.]
- 7. Number of intra-operative parathyroid hormone (PTH) assays sent
 - a. Number of intra-operative parathyroid hormone assays sent during the procedure [Time Frame: Immediate. During PTx procedure.]
- 8. Duration taken to identify first parathyroid gland
 - a. Duration taken to identify 1st parathyroid gland in PTx procedure – timed from skin incision to finding PG. [Time Frame: Immediate. During PTx procedure.]
- 9. Duration taken to identify last parathyroid gland
 - a. Duration taken to identify last parathyroid gland in PTx procedure – timed from skin incision to finding the last PG. [Time Frame: Immediate. During PTx procedure.]
- 10. Duration of parathyroidectomy (PTx) procedure
 - a. Duration of PTx procedure – timed from skin incision until the surgeon notifies the anesthesia team to awaken the patient [Time Frame: Immediate. During PTx procedure.]
- 11. Duration taken for intraoperative parathyroid hormone (PTH) to normalize
 - a. Time taken for PTH to attain cure criteria or normalize - timed from skin incision until the PTH levels drops > 50% of its baseline value and/or PTH drops < 65 pg/ml or 6.9 pmol/L. [Time Frame: Immediate. During PTx procedure.]
- 12. Number of nights spent in the hospital after parathyroidectomy
 - a. Number of nights spent for postoperative recovery in the hospital after the surgical procedure. [Time Frame: 0-72 hours after PTx procedure.]
- 13. Number of 'false positive' tissues excised by surgeon
 - a. Number of tissues that were excised by surgeon assumed to be parathyroid tissue, but is later validated as nonparathyroid tissue (false positive) by histology [Time Frame: Immediate to 10 days after PTx procedure.]
- 14. Number of doctor visits/emergency department visits or hospital admissions

- a. Number of doctor visits/emergency department visits or hospital admissions due to persistent hypercalcemia and/or associated symptoms after parathyroidectomy procedure [Time Frame: Up to 6 months after PTx procedure.]
15. Number of patients who have had repeat parathyroidectomy (PTx) procedure
 - a. Number of patients with repeat PTx procedure performed after the current procedure [Time Frame: 6 - 12 months after PTx procedure.]

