Continuous variables will be reported using medians and interquartile ranges (IQRs). Categorical variables will be reported using counts, percentages, and their 95% confidence intervals (CIs). Comparisons of the NIRAF and control parathyroidectomy groups for primary and secondary outcomes will be done using (a) 1-sided χ^2 or Fisher tests for categorical variables and (b) 2-tailed Student's t-test or Wilcoxon's test for continuous variables (depending on distribution of data). To analyze factors that influence the primary outcome assessed for this study, i.e., number of frozen sections specimens (or PTH aspirate) sent for analysis, a generalized linear mixed models will be used. The following variables will be considered as fixed effects for the study model: (i) nature of the intervention (NIRAF or control), (ii) age, (iii) BMI, (iv) number of intraoperative PTH assays, (v) number of diseased parathyroid glands seen, and (vi) type of parathyroid surgery (focused parathyroidectomy or bilateral neck exploration). The multivariate analysis based on this model will generate the respective odds ratios and their 95% CIs for the aforementioned factors that are being considered. A p-value ≤ 0.05 based on the statistical analysis for continuous/categorical variables under the primary and secondary outcomes measured in this study will be considered as significant.

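### A shared *and/or* can count one patient as both PTH failure (outcome 1) and PTH normalised (outcome 11), and outcome 11 has no rule for patients who never normalise

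*Combined protocol and SAP*

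**What the plan says.** All references are to the combined protocol and SAP.

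- **Section 2.0, Secondary Outcome Measure 1** counts immediate persistent disease as intra-operative PTH that does not normalise, defined as "failure of PTH to drop > 50% of its baseline value at final intra-operative PTH assay and/or failure of PTH to drop" below 65 pg/ml.
- **Section 2.0, Secondary Outcome Measure 11** is "Time taken for PTH to attain cure criteria or normalize", with the clock running from skin incision "until the PTH levels drops > 50% of its baseline value and/or PTH drops < 65 pg/ml or 6.9 pmol/L". Unlike outcome 1, it does not say which assay counts.
- **Section 10.0, Analysis Plan** provides a "2-tailed Student's t-test or Wilcoxon's test for continuous variables", chosen according to the distribution. It gives no value, rank, censoring rule or exclusion for a patient who has no outcome 11 time.
- **Section 6.0** lists the data to be compiled. PTH appears there only at 5-14 days and 6 months after surgery; intra-operative values and assay times are not named.

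**The concern.** Failure and success should be complements. Here both are built from the same two criteria with the same connective, and the negation of a statement joined by *or* is a statement joined by *and*. So one meaning of *and/or*, applied in both places, cannot give complementary definitions. The immediate failure rate and the time to normalisation may then disagree about the same patient, and the reading could be settled after the data are seen.

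The second problem is separate. Outcome 1 exists to count patients whose PTH does not normalise during surgery, so the plan foresees them, yet outcome 11 gives them no value. If they simply drop out of a t-test or Wilcoxon test, the arms are compared within a subset formed after randomisation, by something the device may change. A device that turned some failures into late successes would add long times to its own arm, while the control arm's failures would disappear from the comparison.

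**Working it through.** There is no figure in the plan to reproduce on this point. The check is one of logic, followed by illustrations.

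**1. The definitions.** Let B be baseline PTH and x the final value, both in pg/ml. Write A for x < B/2 (a drop of more than 50%) and C for x < 65.

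| Reading of *and/or* | Failed (outcome 1) | Normalised (outcome 11) | Patient meeting exactly one criterion |
|---|---|---|---|
| *or* in both | not A or not C | A or C | both failed and normalised |
| *and* in both | not A and not C | A and C | neither |
| *or* in 1, *and* in 11 | not A or not C | A and C | failed only |
| *and* in 1, *or* in 11 | not A and not C | A or C | normalised only |

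Only the two mixed readings are consistent, and they require the same words to mean different things in two items of one list.

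**2. The affected range.** Exactly one criterion is met when min(B/2, 65) ≤ x < max(B/2, 65), a range of width |B/2 − 65|. The baselines below are illustrations; the documents give no PTH distribution.

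| B | Affected final values | Width |
|---|---|---|
| 80 | 40 to <65 | 25 |
| 100 | 50 to <65 | 15 |
| 130 | none | 0 |
| 150 | 65 to <75 | 10 |
| 200 | 65 to <100 | 35 |
| 300 | 65 to <150 | 85 |

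For example, B = 200 and x = 70 is a 65% drop but not below 65. B = 100 and x = 60 is below 65 but only a 40% drop.

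**3. Timing.** Outcome 1 looks at the final assay and outcome 11 at attainment. Even with a single criterion, a patient whose PTH meets it and then rises above it by the final assay would be normalised in outcome 11 and failed in outcome 1.

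**4. Patients with no outcome 11 value.** The documents give no intra-operative rate. Section 1.0 says that failure to identify or localise the diseased gland can occur in 5-10% "of cases resulting in failed parathyroidectomies". Taking that range as a stand-in (an assumption), 55 × 0.05 = 2.75 to 55 × 0.10 = 5.5 patients per arm, or 5.5 to 11 of 110, would have no time.

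**5. Effect of leaving them out.** Let θ be the chance that a control patient takes longer than a NIRAF patient, plus half the chance of a tie. Values above 0.5 favour NIRAF. Assume 10% of control patients and 5% of NIRAF patients never normalise.

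*Case (a): normalisers' times have the same distribution in both arms.*
- Normalisers only: θ = 0.500.
- Worst rank for the others: 0.5 × 0.90 × 0.95 + 0.10 × 0.95 + 0.5 × 0.10 × 0.05 = 0.4275 + 0.095 + 0.0025 = 0.525.

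*Case (b), extreme: the extra 5% who normalise under NIRAF do so later than everyone else.*
- Normalisers only: 0.5 × 0.90/0.95 = 0.474.
- Worst rank: 0.5 × 0.90 × 0.90 + 0.10 × 0.95 + 0.5 × 0.10 × 0.05 = 0.405 + 0.095 + 0.0025 = 0.5025.

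A simulation of 2,000,000 pairs for case (b) gave 0.4736 and 0.5025.

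**The case against.** The strongest reply is that this is an ambiguity and not a contradiction. A reader might infer that the plan definitely classes every one-criterion patient both ways. It does not: the double count needs inclusive *or* in both places, and a mixed reading removes it. Nor does the wording of outcome 11 about cure criteria or normalising settle the matter, since it may be two names for one endpoint. This stands, and it limits the claim to what *can* happen. It does not rescue the definitions, because no section chooses a reading and neither like-for-like reading works.

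A reader might also infer that the plan orders non-normalisers to be excluded. Section 10.0 is silent, and the Wilcoxon test it names can accommodate worst ranks. The defect is an omission; exclusion is only what happens by default when a patient has no value.

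Third, the reversal in case (b) is a selected case. With about 50 normalisers per arm, the null standard error of θ is √[(50 + 50 + 1)/(12 × 50 × 50)] = 0.058, so 0.474 lies under half a standard error from 0.5, and 0.5025 is close to no difference. Case (a) shows dilution and not reversal. The rates come from a failed-operation figure. All of this stands: the example shows a possible direction of bias and forecasts nothing.

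**Conclusion.** The point holds as an unresolved definition plus a missing handling rule. Under either like-for-like reading of *and/or*, patients meeting exactly one PTH criterion are classified inconsistently across outcomes 1 and 11. The affected range is given above; the number of patients in it cannot be computed from the documents. Separately, outcome 11 has no value for patients who never normalise, and the default comparison would be among normalisers only. Under assumed rates of 10% and 5%, that dilutes a benefit (0.500 against 0.525) or, in the extreme case, reverses its direction (0.474 against 0.5025).

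Two of the 15 secondary outcomes are affected. It would be wrong to read this as undermining the trial's main result: the primary outcome is the count of frozen sections or PTH aspirates, and neither it nor the sample size uses these definitions. The two items should still be reconciled before analysis. Which PTH criterion is clinically right is not judged here.

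**What to change.** 1. Reconcile the two items in Section 2.0 by stating one intra-operative PTH criterion, chosen by the investigators, and using it in both.
2. Define outcome 1 as the exact negation of that criterion at the final assay.
3. Define outcome 11 as the time from incision to the first assay meeting the criterion, among patients who still meet it at the final assay. This also settles the patient whose PTH falls and then rises.
4. In Section 10.0, analyse outcome 11 with the Wilcoxon test already named. Give the worst rank to every patient with assays who is a failure under outcome 1, and report the number per arm.
5. Treat patients with no intra-operative assay as missing, not as failures, and report their number per arm.
6. Add intra-operative PTH values and assay times to the compiled-data list in Section 6.0. Outcomes 1 and 11 cannot be derived without them, and outcome 7 secures only a count: "Number of intra-operative parathyroid hormone assays sent during the procedure".

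A time-to-event analysis censoring non-normalisers at the end of surgery may look attractive, because outcome 10 already records that time. It is not a sound substitute: it treats patients known to be failures as though their later course were merely unobserved, while outcome 11 is confined to the procedure.

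The cost is rewording two outcomes, two handling sentences and one addition to the data list. No assay is added beyond what outcomes 1 and 11 already imply. The downside is that outcome 11 becomes a rank comparison and no longer yields a difference in mean time.

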6.0 Study Procedures

For patients assigned to the study arm, the surgeon will use the PTeye as an intraoperative tool to identify if a suspect tissue is a parathyroid or not, during the parathyroid surgery. The surgeon will first take 5 baseline NIRAF measurements on the thyroid gland (or neck muscle, if thyroid is absent) using the disposable sterile fiber probe that is connected to the PTeye console (see Figure 1), as per device functionality requirements. The subsequent step would involve touching the target tissue in the neck with the fiber optic probe, following which the PTeye will indicate to the surgeon if the tissue is parathyroid or not. Parameters which are displayed on the PTeye console – Baseline values, Detection Intensity, Parathyroid Detection Ratio – will be recorded for each patient enrolled in the study arm. PTeye indicates that a tissue is parathyroid if it displays the 'Parathyroid Detection Ratio' is greater than 1.2. The rest of the surgical procedure will follow according to standard protocol.

For patients assigned to the control arm, the surgeon will not use the PTeye and will proceed with the parathyroid surgery as usual, while relying solely on her/his surgical experience in identifying the parathyroid glands during the operations.

Figure 1. A commercial fiber probe-based system (PTeye, [REDACTED]) for detecting near infrared autofluorescence (NIRAF) utilized for intraoperative parathyroid gland identification. PTeye consists of 1) the console that has a display and indicates to the surgeon if a tissue is parathyroid or not, 2) a detachable fiber optic probe, and 3) a foot-pedal which is activated by the surgeon for tissue NIRAF measurements.

De-identified information regarding (i) patient demographics, (ii) duration of surgery, (iii) number of frozen section (or PTH aspirate) analysis performed, (iv) frozen section (or PTH aspirate) and permanent histology reports of all excised tissues, (v) blood calcium levels (before surgery, 5-14 days after surgery and 6 months after surgery), (vi) parathyroid hormone (PTH) levels (5-14 days after surgery and 6 months after surgery) and (vii) postsurgical complications, if any and history of ER visits or hospitalization or repeat surgeries due to high or altered calcium levels, will be compiled for all enrolled patients. These parameters would then be compared between the study arm and the control arm to truly gauge the impact or value of a device like PTeye for parathyroid surgeries.

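### Secondary outcome 4 counts glands by a different, unconfirmed rule in each arm, so a between-arm difference cannot separate extra glands truly found from false device calls

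*Combined protocol and SAP*

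**What the plan says.** Section 2.0, secondary outcome 4, is the overall number of parathyroid glands identified, with the counting rule set by arm: "Experimental Group: Glands identified with naked eye + NIRAF; Control Group: Glands identified with naked eye". Its time frame is the operation itself. Outcome 5 is "Number of parathyroid glands identified with NIRAF, which was not seen with surgeon's naked eye", also timed during the operation.

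Section 6.0 states when the device calls a tissue parathyroid: "PTeye indicates that a tissue is parathyroid if it displays the 'Parathyroid Detection Ratio' is greater than 1.2". In the control arm the device is not used, and the surgeon proceeds "relying solely on her/his surgical experience in identifying the parathyroid glands during the operations".

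Histology enters one outcome as the reference standard. Outcome 13 counts excised tissue that the surgeon took for parathyroid but that is "later validated as nonparathyroid tissue (false positive) by histology", with a window of up to 10 days. Section 6.0 collects "permanent histology reports of all excised tissues" for all enrolled patients. Neither is linked to outcome 4.

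The Analysis Plan in Section 10.0 compares the arms on primary and secondary outcomes, treats p ≤ 0.05 as significant, and makes no exception for outcome 5.

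**The concern.** A gland count compares fairly between arms only if the same thing is counted in both. Here the NIRAF arm has a source of positive calls that the control arm lacks, and no step checks those calls before they are counted. A true extra gland found with the probe is the effect the trial hopes to show. A non-parathyroid tissue that reads above the threshold is an error. On the natural reading of outcome 4, both add one to the count.

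The outcome bears directly on aim (i), intraoperative identification of parathyroid tissue, although the protocol does not map outcomes to aims and outcomes 5, 6 and 13 bear on it too. The definitions also allow one excised tissue to count as a gland under outcome 4 and as a false positive under outcome 13. A favourable result on outcome 4 could then be set aside as an artefact, and the data as defined could not answer that criticism.

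Outcome 5 has a simpler problem: it has no meaning in an arm where the device is not used, so a between-arm test of it is not interpretable.

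**Working it through.** **Does the definition admit false device calls?**

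1. Outcome 4 joins two sources in the NIRAF arm with a plus sign and names one source in the control arm.
2. Outcome 5 counts glands found with NIRAF that the eye did not see. This makes the additive reading of the plus sign the natural one, though the protocol does not state it outright.
3. Section 6.0 defines a positive device call as a detection ratio above 1.2.
4. Neither outcome asks for histology, frozen section or PTH aspirate, and both close at the end of the operation, before permanent histology need be available.
5. Intraoperative checking is expected to be scarcer in the NIRAF arm: the preliminary data in Section 10.0 give 0.1 frozen sections per patient with NIRAF and 0.6 without.

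So false device calls can be counted, in one arm only.

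**How large could the effect be?** The plan states no expected count, SD or power for outcome 4, so there is no figure of its own to reproduce. The inputs are:

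- n = 55 per arm, from Section 10.0 (sized for the primary outcome).
- Two-sided test at 0.05, from Section 10.0.
- False-call rate f = 3% per non-parathyroid tissue probed: an assumption. Section 1.0 credits NIRAF methods with "label-free identification of parathyroid tissues with an accuracy as high as 97" per cent. That is a best case for the modality in general, not split into false positives and false negatives, and not a false-positive rate for this device.
- k = 3, 5 or 10 non-parathyroid tissues probed per patient: an assumption.
- SD of the gland count = 1, with 0.8 and 1.2 as a range: an assumption.

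Spurious shift: d = k × f, giving 3 × 0.03 = 0.09, 5 × 0.03 = 0.15 and 10 × 0.03 = 0.30 glands per patient.

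Standard error of the difference at SD 1: √(2/55) = 0.191.

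Chance of a significant result favouring NIRAF with no true gain: Φ(d/SE − 1.96). For d = 0.30 this is Φ(1.573 − 1.96) = Φ(−0.387) = 34.9%.

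| Shift | SD 0.8 | SD 1.0 | SD 1.2 |
|---|---|---|---|
| 0 | 2.5% | 2.5% | 2.5% |
| 0.09 | 8.5% | 6.8% | 5.9% |
| 0.15 | 16.4% | 12.0% | 9.6% |
| 0.30 | 50.3% | 34.9% | 25.8% |

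Counting significance in either direction at SD 1, the figures are 7.6%, 12.3% and 35.0% against a nominal 5%.

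**Can the bias go the other way?** Suppose visual false positives occur at 0.15 per patient and negative probe readings remove all of them in the NIRAF arm. A simulation with 55 per arm, equal true glands in both arms and 0.15 device false positives per patient gave a mean difference of −0.004, with significance 2.3% in favour of NIRAF and 2.9% against. With 0.09 device false positives the expected difference is 0.09 − 0.15 = −0.06, against NIRAF.

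**The case against.** The strongest reply is that outcome 4 does not say every reading above 1.2 is a gland. Section 6.0 describes a contact probe that the surgeon applies to a suspect tissue, so naked eye plus NIRAF could mean the surgeon's device-aided judgement, which is close to the rule proposed below. That reading is possible, and the protocol should say so if it is meant. It would still leave the calls unconfirmed and outcome 4 unlinked to the histology used in outcome 13.

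A reader might infer that the comparison favours the device by construction. The documents do not support that. Added positive calls can only raise the count, but naked-eye calls are unconfirmed in both arms, and negative readings may lead the surgeon to abandon suspected tissue and so lower the NIRAF count. The net direction depends on behaviour the protocol does not describe.

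A reader might also apply a 3% to 5% false-call rate to 10 tissues touched per patient, get 0.3 to 0.5 spurious glands, and conclude that the test would be falsely significant 35% to 74% of the time. That treats all 10 tissues as non-parathyroid. If 4 of the 10 were true glands (an assumption), the shift would be 6 × 0.03 = 0.18 to 6 × 0.05 = 0.30, and the chance about 15% to 35%. With fewer tissues probed it is lower still.

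Two further replies stand in part. Excised non-parathyroid tissue is already reported in both arms as outcome 13, so a reader would see that error beside outcome 4, but as a separate tally. And testing outcome 5 between arms is probably loose drafting with little practical consequence; one sentence settles it.

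**Conclusion.** The point holds as a cheap improvement to one secondary outcome. What is established from the text is that outcome 4 counts by a different rule in each arm, requires no confirmation, and has no provision for tissue that histology later refutes. That false device calls enter the NIRAF count rests on the natural, but not explicit, reading of outcomes 4 and 5 with the 1.2 threshold. On that reading the comparison cannot separate true extra glands from false calls.

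The size cannot be computed from the documents. The illustration of about 7% to 35% depends wholly on the assumed number of tissues, the 3% rate and SD 1, and assumes that nothing offsets the added calls. It shows that the effect could matter, not that it will. The sample size and the primary outcome, the number of frozen sections or aspirates, do not depend on this definition.

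**What to change.** - Define outcome 4 by one rule in both arms: the number of tissues the surgeon finally judges to be parathyroid, minus excised tissues that permanent histology refutes. Extend its time frame to when histology is available; outcome 13 already allows up to 10 days.
- Do not use frozen section or aspirate as the confirmation, because the trial expects these to differ by arm.
- Add the number of histology-confirmed excised glands as a supporting comparison, noting that it measures excision rather than identification.
- State that outcome 5 is descriptive in the NIRAF arm, with no between-arm test.

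The cost is revised outcome wording and derived counts from data that Section 6.0 already collects in both arms. No procedure, visit or change in sample size is needed. The correction is partial: glands left in place remain unconfirmed in both arms, device-positive tissue among them, and the protocol should state this as a limit. The NIRAF count may come out slightly lower than under the present wording.

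### Secondary outcome 5 is zero by definition in the control arm but is not exempted from the between-arm tests, and no planned analysis reports the opposite disagreement between eye and device

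*Combined protocol and SAP*

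**What the plan says.** Section 2.0 defines secondary outcome 5 as the "Number of parathyroid glands identified with NIRAF, which was not seen with" the surgeon's naked eye. No control-group version of this outcome is given, and confirmation of the gland by pathology or aspirate is not required.

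Section 6.0 states: "For patients assigned to the control arm, the surgeon will not use the PTeye". In the device arm, the console values, including the Parathyroid Detection Ratio, "will be recorded for each patient enrolled in the study arm". A ratio greater than 1.2 is the device's positive call. Frozen section or aspirate results and permanent histology of excised tissue are compiled for all patients.

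The Analysis Plan in Section 10.0 states: "Comparisons of the NIRAF and control parathyroidectomy groups for primary and secondary outcomes will be done using" one-sided χ² or "Fisher tests for categorical variables and" a "2-tailed Student's t-test or Wilcoxon's test for continuous variables". A p-value of 0.05 or less for variables "under the primary and secondary outcomes measured in this study will be considered as significant". Outcome 5 is not exempted.

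**The concern.** There are two linked problems.

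First, a between-arm test needs an outcome that could go either way. Outcome 5 requires a NIRAF identification, and a control patient cannot have one. A significant result would show only that the device was used and sometimes signalled on something the surgeon had not seen.

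Second, eye and device can disagree in two directions, and the plan counts only the one in the device's favour. Aim (i) in Section 2.0 leaves open whether PTeye helps identification. A confirmed parathyroid gland that the surgeon saw and the device read as negative bears on that question as directly as a gland the device added, but no outcome or planned analysis tabulates it.

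At stake is a reported significant gain in glands identified with NIRAF, with a p-value that carries no comparative information and no companion figure for device misses.

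**Working it through.** **Arm size.** The plan states no figure for outcome 5, so the arm size comes from the primary-outcome calculation in Section 10.0 (difference 0.6, SD 0.8, two-sided 0.05, power 95%). n = 2 × (1.960 + 1.645)² × 0.8² / 0.6² = 46.2, so 47 per arm, as the plan states. Then 47 × 1.15 = 54.05, rounded up to the plan's 55.

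**Test of k/55 against 0/55.** Let k device-arm patients have one NIRAF-only gland each, and let all other patients in both arms have none.

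- t-test, k = 4: the means are 4/55 = 0.0727 and 0. The device-arm variance is (4/55)(51/55)(55/54) = 0.0687 and the control variance is 0. SE = √(0.0687/55) = 0.0353, and t = 0.0727/0.0353 = 2.06 on 108 df, giving p = 0.042.
- Wilcoxon, k = 4: U = 4 × 55 + ½ × 51 × 55 = 1,622.5, against an expected ½ × 55 × 55 = 1,512.5. The tie-corrected SD is 54.2. With continuity correction z = 109.5/54.2 = 2.02, giving p = 0.0435.
- k = 3: t-test p = 0.080, Wilcoxon p = 0.082. Four patients (4/55 = 7%) is therefore the smallest such number that reaches significance.
- One-sided Fisher, if the count were reduced to any versus none (the plan does not say so): p = C(55,k)/C(110,k), which is 0.059 at k = 4 and 0.028 at k = 5.
- With 47 per arm the thresholds do not change: k = 4 gives t-test p = 0.041 and Wilcoxon p = 0.043; k = 5 gives Fisher p = 0.028.
- k = 0: the t-test and Wilcoxon have no variation to test, and Fisher p = 1. No data set can put control ahead.

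**What the test fails to distinguish.** As an illustration, suppose device-only and eye-only glands are equally frequent, so that the device is no better a detector than the eye. The documents give no rates, so 0.05 to 0.20 glands of each kind per patient is an assumption (Poisson counts, 55 per arm, 3,000 simulated trials). The last column is an exact test within the device arm that counts both directions.

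| Glands of each kind per patient | Wilcoxon against all-zero control, p ≤ 0.05 | Both directions counted, p ≤ 0.05 |
|---|---|---|
| 0.05 | 28% | 1% |
| 0.10 | 78% | 2% |
| 0.15 | 96% | 3% |
| 0.20 | 99% | 3% |

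**Search for the reverse count.** All 15 secondary outcomes in Section 2.0 were checked.

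- Outcome 4 pools eye and NIRAF in the device arm. A gland seen by eye and read negative adds to that total and does not appear as a miss.
- Outcome 13 counts tissue wrongly excised by the surgeon, which is a different error.
- Outcomes 1–3 (intraoperative, transient and six-month persistent disease) and 15 (repeat surgery) measure consequences in both arms but cannot be attributed to a device reading.
- The Section 10.0 model concerns the number of frozen sections or aspirates only.

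The raw material for the reverse count is collected under Section 6.0. The plan does not say it will be used this way.

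**The case against.** The case on the other side has five parts.

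- **The test comes from a general sentence.** Outcome 4 names both groups and outcome 5 does not, so the authors may have meant outcome 5 as a description of the device arm. That is plausible. Followed as written, however, the analysis rule includes it and attaches a significance threshold, so the exception should be stated.
- **Identification does not rest on outcome 5.** This stands. A reader might infer that the trial's whole assessment of identification can only favour PTeye. The documents do not support that: outcome 4 is a genuine two-arm count, and it could favour control if negative readings led surgeons to abandon true glands.
- **Glands left behind are measured.** This also stands. A reader might infer that the harm from a missed gland goes unrecorded. Outcomes 1–3 and 15 record its clinical consequences in both arms. What is absent is narrower: the device's own miss rate.
- **This is an impact trial of a cleared device, not an accuracy study.** That is a fair argument against demanding a full accuracy analysis. It does not justify reporting one direction of disagreement alone when the data for the other are largely in hand.
- **The miss count will be incomplete.** Correct. Section 6.0 has the surgeon probe suspect tissue. It does not require every eye-identified gland to be probed, or the visual call to be recorded before the reading.

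**Conclusion.** The point holds for one secondary outcome. Outcome 5 is structurally zero in the control arm, and the planned between-arm test on it can only favour PTeye or be null. Four of 55 device-arm patients with one such gland each are enough for p of about 0.04. This conclusion rests on the text and on the stated arm size. The simulation adds only an illustration at assumed rates, and it does not show that the device lacks value as an adjunct to the eye.

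The reverse disagreement is missing from the outcomes and the analysis plan, though not from the data: ratios are recorded and excised tissue is examined.

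The size of the device's miss rate cannot be estimated here. A reader might turn the background's accuracy of up to 97% into a 3% miss rate. Accuracy also depends on specificity and on the mix of tissues probed, and the documents give neither a sensitivity nor the number of glands probed per patient.

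The primary outcome and its sample size are unaffected.

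**What to change.** In the Analysis Plan in Section 10.0:

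1. Exclude outcome 5 from the between-arm tests.
2. Report it descriptively within the NIRAF arm with 95% CIs, restricted to glands confirmed by frozen section, aspirate or permanent histology. Without this restriction a device false positive could be counted as a gain.
3. Beside it, with 95% CIs, report the number of confirmed, eye-identified glands that were probed and read negative at the plan's own threshold of 1.2.
4. Keep outcome 4 as the between-arm comparison for identification.

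The cost goes somewhat beyond SAP wording. Each reading must be linked to its specimen, and the form must note whether the surgeon had already identified the gland by eye. Outcome 5 itself already depends on that note. No extra patients are needed.

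The limitation is that the miss count covers only glands that were both probed and confirmed. It is a selected sample, and the report should label it as such and not present it as the device's sensitivity.
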